A Phase I/II Trial of the Pharmacokinetics, Tolerability, and Safety of Once-Weekly Rifapentine and Isoniazid in HIV-1-infected and HIV-1-uninfected Pregnant and Postpartum Women with Latent Tuberculosis Infection

ABBREVIATIONS AND ACRONYMS

3HP	Rifapentine (900mg) and isoniazid (900mg) weekly for 3 months
3TC	Lamivudine, Efavirenz
9H	INH 300mg daily for 9 months
ACTG	AIDS Clinical Trials Group
AE	Adverse Event
AIDS	Acquired Immunodeficiency Syndrome
ALT	Alanine Transaminase
ART	Antiretroviral Therapy
ARV	Antiretroviral
AST	Aspartate Aminotransferase
AUC	Area Under the Curve
BSV	Between subject variability
cART	Combination ART
CBC	Complete Blood Count
CDC	Centers for Disease Control and Prevention
CFR	Code of Federal Regulations
CI	Confidence interval
CL/F	Clearance
CLIA	Clinical Laboratory Improvement Amendments
C _{max}	Peak Plasma Concentration
CMC	Clinical Management Committee
C _{min}	Minimum Plasma Concentration
CRF	Case Report Form
CRPMC	Clinical Research Products Management Center
CRS	Clinical Research Site
D4T	Stavudine
DAERS	DAIDS Adverse Event Reporting System
DAIDS	Division of AIDS
DAIDS PRO	DAIDS Protocol Registration Office
DDI	Didanosine
desRPT	Desacetyl-rifapentine
DMC	Data Management Center
DNA	Deoxyribonucleic Acid
DOT	Directly Observed Therapy
DSMB	Data and Safety Monitoring Board
EAE	Expedited Adverse Event
EC	Ethics Committee
EFV	Efavirenz
EIA	Enzyme Immunoassay
EQA	External quality assurance
FDA	(US) Food and Drug Administration
FSTRF	Frontier Science and Technology Research Foundation
GCLP	Good Clinical Laboratory Practice

GCP	Good Clinical Practices
HAART	Highly Active Antiretroviral Therapy
HIV-1	Human Immunodeficiency Virus Type 1
IATA	International Air Transport Association
ICF	Informed Consent Form
ICH	International Conference on Harmonisation
IGRA	Interferon Gamma Release Assay
IMPAACT	International Maternal Pediatric Adolescent AIDS Clinical Trials Network
IND	Investigational New Drug
INH	Isoniazid
INR	International Normalized Ratio
IRB	Institutional Review Board
IoR	Investigator of Record
LAR	Legally Authorized Representative
LC	IMPAACT Laboratory Center
LTBI	Latent Tuberculosis Infection
MDR TB	Multi-drug resistant tuberculosis
MOH	Ministry of Health
MOP	Manual of Procedures
MTB	Mycobacterium tuberculosis
MUAC	Middle Upper Arm Circumference
NIAID	National Institute of Allergy and Infectious Diseases
NICHHD	Eunice Kennedy Shriver National Institute of Child Health and Human Development
NIH	National Institutes of Health

Site 31790, Desmond Tutu TB Center

[name], PhD
Director, Paediatric Research
Desmond Tutu TB Centre
Department of Pediatrics and Child Health
Stellenbosch, University South Africa
[contact]
[contact]
Email: [contact]

IMPAACT 2001
A Phase I/II Trial of the Pharmacokinetics, Tolerability, and Safety of Once-Weekly Rifapentine and Isoniazid in HIV-1-infected and HIV-1-uninfected Pregnant and Postpartum Women with Latent Tuberculosis Infection

SCHEMA

- Purpose:** To describe the pharmacokinetics, tolerability, and safety of 12 once-weekly doses of rifapentine (RPT) and isoniazid (INH) in pregnant and postpartum women with latent tuberculosis (TB) and inform the practice on usage of this regimen in the second and third trimesters of pregnancy.
- Design:** Prospective, open-label, multi-center study
- Study Population:** HIV-1-infected and HIV-1-uninfected pregnant women with latent TB and their infants, enrolled in two cohorts based on gestation:
- Cohort 1: Enrolled in second trimester (≥ 14 to < 28 weeks) and on study drug for 12 weeks
 - Cohort 2: Enrolled in third trimester (≥ 28 to ≤ 34 weeks) and on study drug for 12 weeks
- Sample Size:** Up to 82 pregnant women (and their infants) will be enrolled to yield a minimum of 25 evaluable women in each cohort. Within each cohort, enrollment of at least 10 evaluable HIV-1-infected women will be targeted. This sample size is selected to achieve a relative standard error (RSE) of five percent for estimation of clearance.
- Study Treatment:** Twelve directly observed once-weekly doses of RPT (900mg) and INH (900mg) taken with pyridoxine (25 to 100mg). An interim analysis will be performed to assess the clearance of RPT compared to non-pregnant historical controls, and a dose adjustment may be recommended based on this analysis.
- Study Duration:** Approximately 24 months total. Accrual is expected to require approximately 12 months, and each enrolled woman will be followed through pregnancy and 24 weeks postpartum. Infants will be followed for 24 weeks from birth.

Primary Objectives

- To estimate the population pharmacokinetics (PK) (CL/F, absorption, volume of distribution) of RPT and its desacetyl-rifapentine metabolite (desRPT) among pregnant women during the second trimester and third trimester who are receiving once-weekly RPT (900mg or the new study dose, if a dose adjustment is indicated by the interim analysis) and once-weekly INH (900mg).
- To estimate the incidence of serious adverse events (SAEs) related to RPT + INH dosed once weekly for 12 weeks in pregnant women.
- To describe the infant safety outcomes among infants born to women receiving once-weekly RPT + INH.

Secondary Objectives

[figure not shown]
- To estimate the population pharmacokinetics (PK) (CL/F, absorption, volume of distribution) of RPT and its desacetyl-rifapentine metabolite (desRPT) among pregnant women during the postpartum period who are receiving once-weekly RPT (900mg or the new study dose, if a dose adjustment is indicated by the interim analysis) and once-weekly INH (900mg).
- To assess the impact of covariates (gestational age, weight, age, HIV status) on primary PK parameters using population PK modeling.
- To compare RPT and desRPT exposure pharmacokinetic parameters (AUC, C_{max} , C_{min}) for RPT in pregnant and postpartum women versus non-pregnant historical controls, using noncompartmental analyses.
- To determine the RPT dose in pregnancy that achieves similar estimated exposure (AUC) of RPT as non-pregnant adults at standard doses.
- To quantify RPT and desRPT concentrations at delivery among infants born to women receiving once-weekly RPT + INH.
- To describe the tolerability of RPT + INH dosed once weekly for 12 weeks in pregnant and postpartum women.
- To assess incidence of active TB in mother-infant pairs up to 24 weeks postpartum.
- To explore the population pharmacokinetics (PK) (CL/F, absorption, volume of distribution) of INH in HIV-1-infected and HIV-1-uninfected pregnant and postpartum women (i.e., women who are and are not taking efavirenz (EFV)) who are receiving once-weekly RPT (900mg or the new study dose, if a dose adjustment is indicated by the interim analysis) and once-weekly INH (900mg).

Exploratory Objectives

- To quantify RPT and desRPT concentrations in breast milk of postpartum women receiving once-weekly RPT + INH.

IMPAACT 2001
A Phase I/II Trial of the Pharmacokinetics, Tolerability, and Safety of Once-Weekly Rifapentine and Isoniazid in HIV-1-infected and HIV-1-uninfected Pregnant and Postpartum Women with Latent Tuberculosis Infection

Figure 1: Study Visit Schedule - Mothers and Infants

IMPAACT 2001

A Phase I/II Trial of the Pharmacokinetics, Tolerability, and Safety of Once-Weekly Rifapentine and Isoniazid in HIV-1-infected and HIV-1-uninfected Pregnant and Postpartum Women with Latent Tuberculosis Infection

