9.5 Sample Size Justification

9.5.1 Precision of RPT Clearance Estimation

The stochastic simulation-estimation (SSE) methodology for clinical trial simulation and re-estimation was employed to evaluate sample sizes required to evaluate key pharmacokinetic parameters with precision adequate for decision making on use of RPT + INH in pregnancy (60). This methodology simulates the data from a planned trial with proposed design (number of samples, patients), followed by the estimation of the parameters under the true and alternative model. This is repeated at least 1,000 times, and parameter estimates, relative standard error (RSE), and between subject variability (BSV) estimates are assessed. Table 3 below shows that the RSE of the estimated contrast between median clearance in second trimester and median clearance in third trimester (CL_3rd, column 3) reaches a desirable level of 18% for a total evaluable sample size of 50 women. Precision of estimation of other parameters (CL, V, ka) and BSV are seen to be very good for this sample size, and the estimation of between-participant variation achieves reasonable precision at N=50 as well. In general, RSE of 5% for a pharmacokinetic parameter (e.g. CL, V, ka), 10% for impact of covariate (e.g., impact of pregnancy on CL), and 20% for BSV is considered satisfactory. This is based on literature reviews where RSE associated with these parameters are often higher than proposed values here.

Table 3: Evaluation of sample sizes and power

Number of participants	RSE (CL) (%)	RSE, CL_3 rd (%)	RSE (V) (%)	RSE (ka) (%)	RSE (BSV-CL) (%)	RSE (BSV-V) (%)	Power (%)
10	9	39	9	12	36	41	82.2
15	8	33	8	10	33	35	91
20	7	27	7	9	29	32	94.6
30	6	23	6	7	25	27	98.2
40	5	20	5	6	22	24	99.5
50	5	18	4	6	20	22	99.9
60	4	17	4	5	18	19	100
70	4	14	4	5	17	18	100

The power for an interim analysis sample of size 12 has been computed in comparison to a fixed historical value via a likelihood ratio test at the 0.01 level. Using the stochastic simulation and estimation methodology (60) and employing all available historical data, for Type I error rate of 1%, the power to detect an average 25% departure from mean historical value of CL with 12 individuals is 96%.

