Appendix II: Modeling and Simulation Population Analysis Report – Rifapentine

This population pharmacokinetic (PK) analysis estimates the pharmacokinetics of rifapentine (RPT) and its main metabolite 25-desacetyl-rifapentine (25-des-RPT) based on the combined dataset from 4 clinical studies in children, healthy adolescents and adult patients with active or latent tuberculosis infection (LTBI) where rifapentine was administered either as a single dose or weekly: two Phase I clinical studies (children, adolescents) (63, 64), one Phase I/II clinical study (TBTC Study 25) (65) and one Phase III clinical study (TBTC Study 26) (25).

The population PK analysis comprised a total of 1634 rifapentine and 25-desacetyl-rifapentine serum concentrations from 227 children, adolescents and patients with active or latent tuberculosis who received a range of 300-1200 mg oral doses of rifapentine as a single agent (children, adolescents), or in combination with isoniazid (INH) in TBTC Study 25 and TBTC Study 26. Serum concentration data of RPT and 25-des-RPT were modeled simultaneously using a population analysis approach to estimate RPT and 25-des-RPT population PK parameters (mean and inter-patient variability) as well as the relationship between PK parameters and covariates.

The structural model that best described the pharmacokinetics of rifapentine was a 1-compartment model with a transit compartment chain for description of the absorption delay. All clearance and volume of distribution parameters were allometrically scaled using standard exponents (e.g. 0.75 for clearance and 1 for volume). The following typical population estimates (%RSE) of rifapentine pharmacokinetics were obtained: oral clearance (CL/F) for 70kg patient 2.32 L/h (11 %); central volume of distribution (Vc/F) for 70 kg patient 51.7 L (10 %); absorption rate constant (k_a) 1.69 (34) h⁻¹, mean transit time (MTT) 0.62 h (27) and number of transit compartments (n) 1.8 (76). The inter-patient variability was 40% (13 %) for CL/F, 47% (15 %) for V/F and 90% (47 %) for MTT.

The structural model that best described the pharmacokinetics of 25-des-RPT was a 1-compartment model. The typical population estimates (%RSE) of 25-des-RPT apparent clearance (CL_m/F_m) and apparent volume (V_m/F_m) for 70kg patient were 2.05 L/h (10 %) and 21.9 L (7 %), respectively. The inter-patient variability was 64% (18 %) for CL_m/F_m.

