Secondary PK parameters for RPT and des-RPT (area under the curve (AUC), maximum concentration (C_{max}), and minimum concentration (C_{min})) will be derived from the model for pregnant women in the second and third trimesters of pregnancy.

P2001 PHARMACOKINETIC ANALYSIS PLAN

The study data, which provide a mix of longitudinal and cross-sectional observations, will be combined and modeled using nonlinear mixed effects approaches that are widely used in pharmacology research. Nonlinear mixed effects modeling will be performed using NONMEM v7.4. Dataset manipulation and data visualization will be performed using R v3.5.1 and Microsoft Office Excel. Perl-speaks-NONMEM (PsN) v4.8.1 and Xpose4 v4.6.1 will be used for model evaluation.

Exploratory data analysis

Prior to beginning modeling analyses, the following exploratory data analyses will be performed:

- Scatterplots of dependent variable (DV) versus time, stratified by treatment outcome, cohort, or disease status
- Summary statistics including the number of patients, samples, samples per patient, and number of patients with samples at each visit.

Structural model development

The absorption and disposition kinetics of RPT and des-PRT will be described by a one compartment model with first-order (linear) elimination and first-order oral absorption. More complex models with respect to absorption (e.g. transit compartments), distribution, and elimination will be explored if necessary.

Goodness-of-fit diagnostic plots will be used to assess the structural model:

- Observations versus population and individual predictions
- Population, individual, and conditional weighted residuals versus time

Stochastic model development

Exponential error models will be used to characterize the between-subject-variability of the model parameters. A diagonal sigma-structure will be used, and off-diagonal elements may be included.

For continuous data, additive, proportional, and combined (additive and proportional) error models will be used to characterize the residual variability.

The appropriateness of the random error models will be assessed using diagnostic plots:

- Observations versus population and individual predictions
- Population, individual, and conditional weighted residuals versus time
- Observations versus time with population and individual fits
- Histogram of ETA estimates

Model evaluation

Visual predictive checks will be used to evaluate how well the model describes the data.

Infants

Approach

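### Table 3's precision figures imply a between-woman variability of about 30% for clearance and volume, against 40% and 47% in Appendix II, and Section 9.5.1 does not say what was simulated

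*Protocol*

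**What the plan says.** The Schema, under Sample Size, ties the number of women to clearance: "This sample size is selected to achieve a relative standard error (RSE) of five percent for estimation of clearance". Section 9.5.1 supplies the basis by stochastic simulation and estimation: "This is repeated at least 1,000 times, and parameter estimates, relative standard error (RSE), and between subject variability (BSV) estimates are assessed". It does not give the BSV or the residual error that was simulated.

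The 50-women row of Table 3 reads "50 5 18 4 6 20 22 99.9". In order, these are N, then the RSEs of CL, the third-trimester contrast, V, ka, BSV of CL and BSV of V, then power. The text leads with the trimester contrast, which "reaches a desirable level of 18% for a total evaluable sample size of 50 women", and adds: "Precision of estimation of other parameters (CL, V, ka) and BSV are seen to be very good for this sample size". It then names 5% as a satisfactory RSE for a PK parameter, with CL, V and ka as examples.

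The only rifapentine variability in either document is in Appendix II: "The inter-patient variability was 40% (13 %) for CL/F, 47% (15 %) for V/F and 90% (47 %) for MTT". The bracketed figures are the RSEs of those estimates. Clearance and volume in that model were allometrically scaled, so the variability is what remains after body weight. The SAP specifies the form of the variability for the trial's own analysis: "Exponential error models will be used to characterize the between-subject-variability of the model parameters".

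**The concern.** Sampling each woman more often sharpens the estimate of her own clearance and volume. It does not remove the differences between women, and these set a floor on the precision of a typical value. Most of Table 3 lies below the floor that Appendix II implies. The ordering also looks wrong: 47% against 40% should make V less precise than CL at every N, yet Table 3 gives equal RSEs in seven rows and a better RSE for V at N=50.

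CL and V of rifapentine are primary PK outcome measures (Section 9.2.1.1), and Table 3 is the stated precision basis for 50 women. If its input is lower than the protocol's own evidence supports, readers will expect tighter estimates than the trial is likely to give, most clearly for V.

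**Working it through.** **Formula.** With exponential BSV of log-scale standard deviation ω, RSE(typical value) ≥ ω/√N. Equality would need every woman's parameter to be known exactly.

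**Inputs.** 40% (CL/F) and 47% (V/F) from Appendix II; N and the RSEs from Table 3. The percentages can be read in two ways:
- as ω directly: 0.40 and 0.47;
- as log-normal coefficients of variation, ω = √ln(1+CV²): √ln(1.16) = 0.385 and √ln(1.2209) = 0.447.

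**Does N count independent women?** For a variance estimated from N perfectly known values, RSE = √(2/N). At N=50 this is 20.0%, which matches Table 3's RSE for BSV-CL (20%). Comparing with ω/√N at the same N is therefore reasonable.

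**The N=50 row.** CL: 0.385/√50 = 5.45%, or 0.40/√50 = 5.66%; Table 3 has 5%. V: 0.447/√50 = 6.32%, or 0.47/√50 = 6.65%; Table 3 has 4%. The V figure is not reproduced under either reading.

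**All rows.** Floors run from the log-normal reading to the direct reading. Implied BSV is the tabulated RSE × √N. It is an upper limit before rounding, because residual error can only raise the RSE above the floor.

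| N | CL, Table 3 | CL floor | CL implied BSV | V, Table 3 | V floor | V implied BSV |
|---|---|---|---|---|---|---|
| 10 | 9% | 12.18-12.65% | 28.5% | 9% | 14.13-14.86% | 28.5% |
| 15 | 8% | 9.95-10.33% | 31.0% | 8% | 11.54-12.14% | 31.0% |
| 20 | 7% | 8.61-8.94% | 31.3% | 7% | 9.99-10.51% | 31.3% |
| 30 | 6% | 7.03-7.30% | 32.9% | 6% | 8.16-8.58% | 32.9% |
| 40 | 5% | 6.09-6.32% | 31.6% | 5% | 7.06-7.43% | 31.6% |
| 50 | 5% | 5.45-5.66% | 35.4% | 4% | 6.32-6.65% | 28.3% |
| 60 | 4% | 4.97-5.16% | 31.0% | 4% | 5.77-6.07% | 31.0% |
| 70 | 4% | 4.60-4.78% | 33.5% | 4% | 5.34-5.62% | 33.5% |

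On the more lenient reading, after rounding, all eight V rows and seven of the eight CL rows lie below the floor. The exception is CL at N=50. A least-squares fit of ω/√N to each column gives a BSV of 30.9% for CL and 30.4% for V.

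**Allowing for rounding and for uncertainty in Appendix II.**
- V at N=50: a printed 4% can be up to 4.5%, so BSV is at most 4.5% × √50 = 31.8%. The approximate 95% range for Appendix II's value is 47% × (1 ± 1.96 × 0.15), or 33-61%. The implied value lies below it.
- CL at N=50: a printed 5% can be up to 5.5%, so BSV is at most 5.5% × √50 = 38.9%. The corresponding range is 40% × (1 ± 1.96 × 0.13), or 30-50%. The implied value lies inside it.

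**Adding residual error and the trimester contrast.** A linearised information matrix was computed for a one-compartment model with 25+25 women and the sampling times in Sections 6.2 and 6.3. It used CL/F 1.47 L/h (Section 10.3.2) and V/F 51.7 × 60/70 ÷ 1.4 = 31.7 L (Appendix II, scaled to 60 kg and fed). Assumed, because the documents do not give them for Table 3: residual error 10-30%, ka 1.0/h with 50% BSV, clearance 25% higher in the third trimester, and all sparse samples treated as third trimester. The result is 5.5-6.0% for CL and 6.35-6.91% for V. With intensive samples only, V reaches 6.98%.

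**The case against.** The strongest reply is that nothing says Table 3 was built on Appendix II. That report pools 227 subjects: children, adolescents, and adults with active or latent infection, some unfed and some taking crushed tablets. Study 26 contributed one 24-hour sample per subject, so the 47% for V rests mainly on the smaller studies. This trial enrols pregnant women only, with observed dosing after a meal and whole tablets. A lower planning variability is conceivable.

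This stands in part. A reader might infer that Table 3 was miscalculated, and the documents do not support that: a BSV of about 30% would roughly account for both columns, so what is shown is an unstated input at odds with the protocol's own report. The reply does not close the gap, however. Appendix II already reports separate effects for weight, maturation, food and crushed tablets, and the protocol offers no other variability estimate and no reason for a lower one.

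Two further points stand. The 5% level is introduced as a general benchmark and not as a design criterion for V. And no decision rule uses these RSEs: the interim rule in Section 10.3.2 compares median CL/F with a 25% margin.

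**Conclusion.** Table 3 and Appendix II do not agree. At Appendix II's variability, V at 50 women has an RSE of at least 6.3-6.7%, against 4% in the table. That is 26-33% above the protocol's 5% benchmark (6.32/5 and 6.65/5). This result needs only the BSV and N.

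For CL the floor is 5.45-5.66%, or about 5.5-6% with residual error and the trimester contrast under the assumptions above. The 5% headline is borderline to slightly optimistic.

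A reader might go further and conclude that the stated basis for 50 women fails for clearance, or that the trial is too small. The documents do not support either. 5.45% rounds to 5% on a standard reading of the 40%, any BSV up to 38.9% would do the same, and Section 9.5.1 leads its case for 50 with the trimester contrast.

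The CL figures assume that all 50 women inform one typical clearance. If each cohort of 25 stood alone, the floor would be 0.40/√25 = 8.0%.

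**What to change.** Rerun the Section 9.5.1 simulation with 40% for CL/F and 47% for V/F, or state the BSV and residual error actually used and justify a BSV below Appendix II. Then restate Table 3 and the Schema sentence. Under Appendix II's variability the expected figures at 50 women are about 5.5-6% for CL and 6.5-7% for V. Qualify the favourable statement about precision in Section 9.5.1 as it applies to V. Regenerate the other columns in the same run so that the table rests on one set of inputs.

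A row for the desacetyl metabolite would be informative, since Appendix II gives 64% variability for its clearance, but it is optional because the protocol sets no precision target for it.

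The cost is one repeat simulation and some wording, with slightly less favourable stated figures. Sample size and conduct do not change.

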1 INTRODUCTION

1.1 Background

An estimated two billion persons carry latent *Mycobacterium tuberculosis* (MTB). Treatment of latent tuberculosis infection (LTBI) is critical to global tuberculosis (TB) control and elimination (1, 2). Globally, the most commonly used current LTBI treatment regimen is six to nine months of INH (3, 4). Treatment completion rates of this regimen, however, are suboptimal, ranging from 5-64% in high-burden TB settings (5-7). Furthermore, potential concerns about the selection of drug resistance and drug toxicity, particularly hepatotoxicity, have hampered implementation of this regimen (8-10).

Pregnant women: LTBI and its treatment

Prevalence of latent LTBI in pregnant women is similar to that of the general population. Studies report a prevalence of 18%–34% among HIV-negative pregnant women in India and up to 49% in HIV-positive pregnant women in South Africa (8, 11). Pregnant women are at increased risk of progressing from latent LTBI to active tuberculosis (TB) because pregnancy suppresses the Th1 immune response (12-14). Symptoms of active TB may not be seen until after delivery, when Th1 suppression reverses and symptoms are exacerbated (13). A large study recently found that early postpartum women are twice as likely to develop TB as non-pregnant women, suggesting that biologic changes in pregnancy and postpartum influence TB epidemiology (15-19).

The World Health Organization (WHO) currently recommends treating LTBI with daily INH for all HIV-infected pregnant women, but few programs have implemented this policy. Adherence and toxicity concerns remain the main barriers to treatment. Adherence rates for daily INH among postpartum Hispanic women in the US, for example, are as low as 6-21% (20). Pregnancy and infant outcomes of women taking INH for active TB treatment are comparable to normal pregnant women not receiving TB treatment, but toxicity concerns persist due to the suboptimal quality of existing studies (21). NIH-funded studies are under way to assess the optimal timing of initiation of INH for TB prophylaxis for HIV-1-infected women (IMPAACT P1078), the pharmacology of first-line TB drugs for TB disease in HIV-1-infected and HIV-1-uninfected pregnant and postpartum women (IMPAACT P1026s and R01HD06435), and pregnancy and treatment outcomes among pregnant women with tuberculosis and HIV (R01HD06435).

The US Centers for Disease Control and Prevention (CDC) recommends the use of either nine months of daily INH monotherapy or a newer regimen of three months of weekly INH and RPT. The INH/RPT regimen is recommended in otherwise healthy patients over the age of 12 years who have LTBI. Though the CDC states that the regimen can be considered in other populations when it offers “practical advantages,” the regimen is not recommended in pregnant women, because the safety of the regimen in pregnancy is unknown. This study aims to address this gap in knowledge.

Pharmacokinetics in pregnancy

The physiologic changes associated with pregnancy can impact drug disposition significantly. Gastrointestinal motility, stomach pH, protein binding, hepatic metabolism, and renal blood flow are all altered by pregnancy and can affect drug absorption, distribution, metabolism, and clearance. Pregnant women experience increased gastrointestinal transit time, which can alter the extent of drug absorption. They also have decreased albumin, which can affect protein binding and drug distribution, as well as free drug concentrations. Moreover, progesterone increases CYP3A4 activity, while estrogen inhibits CYP1A2 and CYP2C19 (22, 23). The combination of these effects complicates dosing regimens for many medications. In HIV management, for example, the dose of lopinavir and darunavir need to be doubled

during pregnancy, but only during the third trimester (24). Clearly, given the complex physiologic changes that occur with pregnancy, a thorough understanding of the pharmacokinetics of new drugs or regimens in this population is needed before they can be administered safely and effectively to pregnant women.

